Furthermore, few studies include formal follow-up procedures related to successes and failures implementing new routines or strategies. Our prior research highlights the importance of individualized feedback during routine family activities. In a small pilot trial of the Mealtime PREP intervention, we found that those children whose parents received feedback during actual family meals were significantly more likely to respond to treatment than those who had received feedback based on parent report. Occupational therapists are uniquely trained to examine the dynamic transaction between the person (family), environment, and activity that they are engaged in to provide customized feedback or recommendations to support optimal performance. Evaluation of this dynamic interplay is lacking in current health promotion interventions of early childhood; the Mealtime PREP intervention provides a systematic

framework to deliver this feedback.

In our early pilot work, the Mealtime PREP intervention empowered parents from middle to high-income families to increase the frequency of family meals, feel confident about managing daily meals, and change daily mealtime routines. However, this study focused on children with Sensory Food Aversions and our convenience sample was homogenous and lacked diversity. Because of the complex barriers faced by low-income families, further investigation is required to determine how to best serve these families. Despite economic, attitudinal and accessibility limitations, longitudinal surveillance of this population has revealed that positive parenting interventions to prevent behavioral issues and aggression appear to have a protective capacity against obesity. While not the primary intent of these interventions, this evidence provides a signal that early intervention focused on parent education, empowerment, and behavior change is a promising approach for obesity prevention. While we are not able to test whether the Mealtime PREP intervention effectively prevents obesity over a 12-week period, the purpose of this trial is to gather data to optimize our approach and meet the needs of low-income families for future trials with long-term follow-up.

**Study Objectives:** The purpose of this pilot project is to trial the Mealtime PREP intervention program with a sample of low-income families.

Specifically, we aim:

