1. To examine the feasibility and acceptability of the Mealtime PREP intervention among low-income families with a preschooler.
2. To estimate the effects of Mealtime PREP on dietary variety, nutrition, and mealtime behaviors of low-income preschoolers.

**Study Design& Methods:** We plan to use a prospective, repeated-measures study design with data collection occurring at baseline, 6 weeks (post-intervention), and 12 weeks (follow-up). Twenty low-income families with a preschooler will be recruited from waiting rooms and/or staff referral at local WIC, Head Start, and pediatric primary care offices. Interested parents will undergo basic screening procedures (i.e. providing responses to screening questions to determine eligibility) prior to being consented to participate in the study.

After eligibility has been confirmed, interested parent participants will undergo the consent process with a trained research assistant and/or the principal investigator in the home environment or an agreed upon alternative in the community. Following informed consent, baseline assessments (including video-recording a typical child meal) will take place. If the child meal is of average length (approximately 20 minutes), this session will last approximately 60-90 minutes. Additionally, they will be asked to complete a 3 day food diary where they log their child's food intake for three days.

Trained research interventionists will then schedule six weekly sessions to take place in the family home or an agreed upon alternative in the community. Each session will last approximately one-hour and will include didactic and practice portions with the therapist demonstrating techniques during a child meal and providing feedback as needed. The entire session will be video-recorded by the interventionist.

Mealtime PREP – Parent Experience: Parents are trained to deliver each intervention component during mealtimes using a step-wise, behavioral activation approach. The parent-

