NutriSTEP and NutriSTEP Toddler Child Risk of Nutritional Deficiency 17 item, validated screen for young children (1–5 years) that categorizes risk of nutritional deficiency into 3 categories (low, moderate, and high).

Parenting Stress Inventory-Short Form Parental Stress Validated tool to assess and categorize parental stress.

**Eligibility Criteria:** Families will be eligible for participation if they have a child in the age range of two to five years old and reside in a low-income household (as specified by income within the range to qualify for WIC services). Parent participants will be eligible for participation if they are > 18 years old, speak English, read at a 6th grade level, and agree to deliver intervention during daily meals.

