## Statistical Considerations

**Data Analysis:** Specific Aim 1: To examine the feasibility and acceptability of the Mealtime PREP intervention among low-income families, we will rely on descriptive statistics (raw scores, frequencies, and percentages) to determine if each benchmark of feasibility has been met. Specific Aim 2: To estimate the effects (child dietary variety, nutrition risk, parental stress) of the

Mealttime PREP intervention, we will calculate effect sizes (Cohen's  $d$ ) based on mean scores of the sample at each time point. Effect sizes will be used to predict effects among low-income families and calculate appropriate sample sizes for future studies. For each outcome of interest, we will run exploratory paired t-tests ( $\alpha = .05$ ) using IBM SPSS Statistics, Version 24. If the data is not normally distributed or if there are outliers upon data exploration, we will switch to equivalent non-parametric tests (e.g. Wilcoxon Signed-Rank). These results will serve as a signal of the ability of this intervention to change behavior over time.

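### Aim 2 labels an uncontrolled pre-post Cohen's d from about 20 families as the effects of Mealtime PREP and offers it for sizing future studies, without a confidence interval

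*Combined protocol and SAP*

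**What the plan says.** Study Design & Methods describes a single group of twenty families, measured at baseline, 6 weeks and 12 weeks. No comparison group appears anywhere in the document.

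Aim 2 under Study Objectives is "To estimate the effects of Mealtime PREP on dietary variety, nutrition, and mealtime behaviors of low-income preschoolers". The Data Analysis text under Statistical Considerations repeats that label: "To estimate the effects (child dietary variety, nutrition risk, parental stress) of the" intervention. The method is Cohen's d "based on mean scores of the sample at each time point", and its use is then stated: "Effect sizes will be used to predict effects among low-income families and calculate appropriate sample sizes for future studies".

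Exploratory paired t-tests at alpha .05 follow. If the data are non-normal or contain outliers, "we will switch to equivalent non-parametric tests (e.g. Wilcoxon Signed-Rank"). The section closes: "These results will serve as a signal of the ability of this intervention to change behavior over time". Neither a confidence interval nor the SD that goes into d is mentioned.

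**The concern.** The quantity named and the quantity computed are different. Without a comparison group, d measures how families changed, not how much of that change Mealtime PREP caused. Children aged two to five may change over 12 weeks without any intervention. The food diary is completed by the caregiver, who is also the person being trained, so reporting may shift as well. The documents give neither size nor direction for untreated change.

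A d from about 20 families is also imprecise, and the plan produces no interval to show it. This matters because planning later work is a declared output of the pilot. The Scientific Background section says that "the purpose of this trial is to gather data to optimize our approach and meet the needs of low-income families for future trials". If a later trial took d at face value, it could be much too small or much too large.

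**Working it through.** The plan gives 20 families without a calculation, so there is no figure to reproduce. The checks below size the consequence.

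**Inputs from the documents:** 20 families, one group, alpha .05, Cohen's d.

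**Assumed, because the documents do not say:** a future trial with two equal arms, two-sided alpha .05, 80% power and an unadjusted comparison of follow-up scores; a d of 0.5; a baseline-to-follow-up correlation r of 0.3 to 0.7; and the sizes of untreated change in step 4.

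**1. Precision of d on the paired scale.**
- t = d × √n = 0.50 × √20 = 2.236, with 19 degrees of freedom.
- Inverting the noncentral t gives noncentrality limits of 0.127 and 4.293.
- Dividing by √20 = 4.472 gives a 95% CI of 0.03 to 0.96.

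**2. Sample size for a true d of 0.5.**
- Normal approximation: n per arm = 2(1.96 + 0.84)² / d² = 62.8, so 63.
- The noncentral t (2n − 2 degrees of freedom, noncentrality d√(n/2)) gives 64. This figure is used below.

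**3. What pilots of 20 would ask for.** Pilots were simulated from a bivariate normal distribution with true d 0.5, using the baseline SD and excluding none.

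| r | 10th to 90th percentile of d | n per arm at those values |
|---|---|---|
| 0.3 | 0.16 to 0.90 | 607 to 21 |
| 0.5 | 0.21 to 0.85 | 348 to 23 |
| 0.7 | 0.275 to 0.78 | 209 to 27 |

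The sample sizes use unrounded percentiles. All compare with 64 needed.
- Because n varies as 1/d², a pilot asks for half the needed n or less when d is about 0.71 or more (0.5 × √2). This happens in 17% to 24% of pilots, and a trial of 32 per arm has about 50% power.
- A pilot asks for at least double, or gives d of zero or below, in 20% to 29%.
- With a baseline-adjusted future analysis at r = 0.5, the range is 18 to 261 per arm against 49 needed, so the conclusion does not depend on that choice.

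**4. No comparator.** Take an observed d of 0.5 and a trial of 64 per arm.

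| Assumed untreated change (SD) | Net effect | Consequence |
|---|---|---|
| +0.1 | 0.4 | power 61% |
| +0.2 | 0.3 | power 39% |
| +0.3 | 0.2 | power 20% |
| −0.1 | 0.6 | 45 per arm enough |
| −0.2 | 0.7 | 34 per arm enough |
| −0.3 | 0.8 | 26 per arm enough |

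**5. Which SD (a clarity point only).** With equal SDs at both times, the SD of change is √(2(1 − r)) times the time-point SD: 1.18, 1.00 or 0.77 times at r = 0.3, 0.5 or 0.7. The plan's reference to time-point means suggests a time-point SD, while its test is paired. The scale suited to a later trial depends on that trial's analysis.

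**The case against.** The strongest reply is that this is a pilot, its tests are called exploratory, and its results are to serve as a signal. No success criterion or participant procedure in this trial depends on d, and any harm needs a later team to adopt it unchanged. That lowers the weight of the point but does not remove it. The word exploratory is attached to the t-tests. The closing sentence can be read as covering the effect sizes too, but what it signals is the intervention's ability to change behavior, which is again causal. Neither expressly limits the sentence on prediction and sample size.

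It is also fair to say that the figures above illustrate the issue and are not evidence about this trial, since true d, r, the future design and the untreated change are all assumed.

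Four stronger readings are tempting, and the documents do not support them:
- That the plan commits to sizing on a bare point estimate. It states an intended use and gives no formula, power or future design, so point-estimate use is an inference. It is a natural one, because the plan names no interval or other planning quantity.
- That d will overstate the effect. Nothing in the documents fixes the direction of untreated change.
- That 20 families is too few. No precision or power target is stated against which to judge it.
- That the unnamed SD would leave a later trial underpowered. The scale difference is real, but its consequence depends on an analysis not yet chosen.

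**Conclusion.** The point holds for the label and the declared use. Following the section as written would report within-group change as the intervention's effects and hand it on for planning with no measure of its uncertainty. The imprecision at n = 20 is substantial (0.03 to 0.96 around a d of 0.50). The range of about 23 to 348 per arm is conditional on d being used as a point estimate under the stated assumptions. The bias from having no comparator is of unknown sign and size. The harm is downstream, the feasibility aim is untouched, and the remedy is cheap, so this should be corrected but does not call the pilot itself into question.

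**What to change.** In Statistical Considerations, Data Analysis, keep the Aim 2 list of outcomes and replace the effect-size wording with:

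> For each of these outcomes we will report mean within-family change from baseline to each follow-up and the standardised change (mean change divided by the baseline SD), each with a 95% CI, together with the SD at each time point and the baseline-to-follow-up correlation. Where the Wilcoxon signed-rank test is used we will report the Hodges-Lehmann estimate of change with its 95% CI. These describe within-group change and are not estimates of a treatment effect. The observed d will not by itself set the sample size of future studies; these will use a justified target difference with the SD and correlation from this pilot and their 95% CIs as a sensitivity range.

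In the closing sentence, describe the results as a signal of change in behavior over time alongside the intervention. Align the wording of Aim 2 under Study Objectives.

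Naming the baseline SD is a reporting choice. The SDs and the correlation let a later planner convert to another scale. The sensitivity range is needed because these inputs are uncertain too. At n = 20 the 95% limits of an SD are 0.76 to 1.46 times its estimate (chi-square, 19 degrees of freedom). For a fixed difference of 0.5 estimated SD, that moves the requirement from 38 to 135 per arm. A correlation of 0.7 has a 95% CI of 0.37 to 0.87 (Fisher z).

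The cost is a little more analysis of data already being collected, less favourable wording, a reworded objective, and a target difference that must be justified when a future trial is planned. The documents do not give one.

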training prong of the Mealtime PREP intervention incorporates four active ingredients of behavioral activation (1. skills training; 2. goal-setting; 3. activity scheduling; and 4. activity monitoring) to help parents build a family meal routine that is enriched with techniques to promote child nutrition (Figure 1). Trained research interventionists with experience in pediatric occupational therapy will lead six weekly parent-training sessions in the home. During each session a new intervention component (e.g. Family Meals, Positive Reinforcement) to promote healthy child feeding habits will be introduced and parents will be provided direct feedback while practicing new skills during a child meal. Parents will work with the therapist to set-up a plan and set a goal to practice delivering intervention components in the home between parent-training sessions.

**Mealtime PREP – Child Experience:** The child-focused prong of the Mealtime PREP intervention embeds positive reinforcement of healthy eating habits and repeated exposure to targeted healthy foods into a consistent family meal routine. Parents will incorporate intervention components (Family Meals, Positive Reinforcement, Food Exploration and Food Play) into the child's routine sequentially, as they are trained to deliver them. In essence, the parent will provide a predictable family meal routine, encourage active child participation, reward healthy eating habits and redirect unhealthy behaviors to acceptable alternatives. Parents will also model healthy eating habits and demonstrate various ways to learn about healthy foods using exploration and play. The intervention will be customized to accommodate a variety of environments, address unique family barriers and incorporate child-centered play.

Trained research assistants and/or the principal investigator will conduct follow-up assessments within two weeks of intervention completion and approximately 12 weeks following baseline. Each assessment session is predicted to last approximately 60-90 minutes. They will also be provided with a 3-Day Food Diary and Self-addressed envelope at each of these sessions.

Primary outcomes include:

3-Day Food Diary (Caregiver Reported) Child Intake and Variety of Healthy Foods Preferred method of dietary assessment because of a balance between validity and burden. Includes all food consumed and approximate servings for 3 days.

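### Three-visit outcomes are compared two visits at a time, so families without a 12-week value leave the 12-week contrast, which is overstated if loss follows a poor 6-week change

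*Combined protocol and SAP*

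**What the plan says.** Study Design & Methods describes a "prospective, repeated-measures study design with data collection occurring at baseline, 6 weeks (post-intervention), and 12 weeks (follow-up"). It adds that "Twenty low-income families with a preschooler will be recruited"; no control group is described. At both follow-up assessments families take the diary away to return later: "They will also be provided with a 3-Day Food Diary and Self-addressed envelope at each of these sessions".

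Under Statistical Considerations, Data Analysis, Specific Aim 2, "we will run exploratory paired t-tests" for each outcome at a two-sided or one-sided level of .05 (which of the two is not stated). The pairs of visits are not named. If the data are non-normal or contain outliers, "we will switch to equivalent non-parametric tests (e.g. Wilcoxon Signed-Rank"). That is the only analysis contingency. There is no missing-data rule, analysis population or expected dropout.

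In a separate sentence, Cohen's d is to be calculated "based on mean scores of the sample at each time point". These effect sizes are meant to inform the sample size of later studies.

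**The concern.** A paired test needs both members of the pair. For baseline to 12 weeks, a family with baseline and 6-week values but no 12-week value contributes nothing, although its 6-week value shows how it was responding. The diary is the outcome most exposed, because it can go unreturned even when the visit took place.

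The 12-week assessment is the plan's only evidence on whether changes last beyond the post-intervention visit. If families who had done poorly by 6 weeks are the ones missing at 12, the completers' change is too favorable. The plan also leaves open which families enter the visit means behind d, so the test and the effect size reported beside it could describe different sets of families.

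**Working it through.** **Inputs.** From the documents: 20 families, three visits, two-visit tests. The plan gives no expected effect, SD, correlation, power or attrition, so there is no figure to reproduce. Assumed: SD 1 at each visit; equal correlation r of 0.5 or 0.7 between visits; true change 0.5 SD at 6 and 12 weeks; 10% to 35% missing at 12 weeks; baseline and 6-week values complete.

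**1. Who is counted.** The contrast keeps 20 × (1 − m) families: 18, 16 and 14 at m = 10%, 20% and 30%, and 15 at 25%. A family missing only week 6 still counts in baseline to 12 weeks.

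**2. Paired bias when loss follows the observed 6-week change.** Let D6 = Y6 − Y0 and D12 = Y12 − Y0.
- Var(D6) = 2(1 − r).
- Cov(D6, D12) = r − r − r + 1 = 1 − r.
- The slope of D12 on D6 is therefore (1 − r) / [2(1 − r)] = 1/2.
- Paired bias = 1/2 × (mean D6 among retained families − true mean D6).

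With 25% missing, and log-odds of loss rising by 1 or 2 per outcome SD of poorer 6-week change, integrating the logistic loss model over a normal D6 gives:

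| r | log-odds | excess D6 in retained | half = bias | simulated bias (6,000 runs) |
|---|---|---|---|---|
| 0.5 | 1 | 0.213 | 0.107 | 0.106 |
| 0.5 | 2 | 0.319 | 0.159 | 0.164 |
| 0.7 | 1 | 0.135 | 0.068 | 0.069 |
| 0.7 | 2 | 0.218 | 0.109 | 0.105 |

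Relative to 0.5 SD, this is 0.07/0.5 = 14% to 0.164/0.5 = 33%. Across 15% to 35% missing, the simulated bias runs from 0.04 to 0.21 SD.

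**3. Three-visit likelihood estimate.** For this pattern it is the regression of Y12 on Y0 and Y6 among completers, predicted for all 20 families. Its bias is at most 0.005 SD in every setting above.

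**4. Other loss mechanisms.** A second simulation used log-odds 1.5 per SD of the change and r = 0.5:

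| Missing | Loss driven by | Paired bias | Model bias |
|---|---|---|---|
| 10% | observed 6-week change | +0.06 | 0.00 |
| 20% | observed 6-week change | +0.11 | 0.00 |
| 30% | observed 6-week change | +0.16 | 0.00 |
| 10% | unseen 12-week change | +0.12 | +0.08 |
| 20% | unseen 12-week change | +0.23 | +0.16 |
| 30% | unseen 12-week change | +0.33 | +0.24 |

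- *Random loss:* both estimates are unbiased to within 0.002 SD. Precision is almost equal (SD of the estimate 0.255 paired, 0.251 model, at 20% missing).
- *Loss driven by stable level:* write Y_t = a + mean_t + e_t. Then D12 = 0.5 + e12 − e0 and a cancels, so the paired change stays unbiased (within 0.003 SD in simulation at 25% missing). The model conditions on Y0 and Y6, which measure a only with error, and is biased by about +0.04 to +0.09 SD.

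**5. Cohen's d from visit means.** If all available families are used, bias depends on Cov(Y12, D6) = r(6,12) − r(0,12). With equal correlations this is 0, and simulated bias is within 0.004 SD. If r(6,12) is 0.7 to 0.8 and the other two correlations are 0.5, the covariance is 0.2 to 0.3. The visit-mean difference is then overstated by 0.04 to 0.10 SD, and the paired change by 0.15 to 0.26 SD.

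**The case against.** The case for leaving the plan alone is substantial.

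- **Scale.** This is a 20-family, single-group pilot whose first aim is feasibility, and the tests are labelled exploratory. At 25% missing the bias of 0.07 to 0.16 SD is smaller than the sampling SD of about 0.20 to 0.26. Attrition, correlation and loss mechanism are all assumed. This stands, and it limits the severity.
- **Validity of the paired test.** A reader might infer that it is valid only if the retained families are a random subset of the 20. It is not so: retention need only be unrelated to the 12-week change. The Scientific Background describes chronic stressors in these families, and loss driven by such a stable trait would leave the paired estimate unbiased.
- **The model's assumption.** A reader might also infer that it is weaker than the paired test's. Neither contains the other: with loss driven by stable level the model is the biased one, and with loss driven by the unseen 12-week change it keeps about 70% of the bias (0.16 of 0.23).
- **Later sample sizes.** It is tempting to say that the paired bias flows into future trials. Using n per arm = 2(1.96 + 0.84)²/d², planning on 0.60 gives 44 and on 0.50 gives 63. But the plan bases d on visit means, which need not share the paired bias. The documents support an ambiguity here; they do not demonstrate an inflated d.
- **Best case.** The calculations assume every 6-week value is present. Envelopes are used at both follow-ups, and a family returning neither diary gives the model little to work with.
- **Lost protection.** Replacing the paired tests outright would discard the signed-rank fallback.

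What survives is the waste of observed 6-week values, the bias under one plausible mechanism, and the silence on who enters d.

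**Conclusion.** The point holds as a conditional, modest one. The planned tests discard 6-week values from families missing at 12 weeks. If loss follows a poor observed 6-week change, the paired 12-week change is overstated by about 0.07 to 0.16 SD at 25% missing, for a true change of 0.5 SD and correlations of 0.5 to 0.7. A three-visit model is then close to unbiased, provided the 6-week values are in hand. With complete data the two approaches give the same mean change. The documents do not show that attrition will be high or that weaker responders will be the ones lost. The analysis is worth improving because the change is cheap and uses data already collected; the plan as written is not invalid.

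**What to change.** In Data Analysis, Specific Aim 2:

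1. Name the contrasts: baseline to 6 weeks and baseline to 12 weeks.
2. For each continuous outcome, estimate both from one linear mixed model using all observed visits. Use visit as a three-level factor, unstructured covariance within family and small-sample degrees of freedom, and state in advance a simpler covariance to use if the model does not converge.
3. Take the mean change for Cohen's d from that model, and state which SD standardizes it and how many families contribute at each visit.
4. Keep the paired t-test, or the signed-rank test under the existing trigger, as a sensitivity check among families with both values.
5. Do not apply the linear model to the three NutriSTEP risk categories.
6. Report the 6-week change separately for families with and without a 12-week value, and add a sensitivity analysis for loss that depends on the unseen 12-week value.

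The cost is a paragraph of text and a standard model run, with no new data. The downsides are an assumption that loss depends on observed data, only partial protection when it depends on the unseen 12-week value, and little gain for families who return neither follow-up diary.
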